- 7) A condition requiring systemic treatment with corticosteroids (>10 mg daily prednisone equivalent) or other immunosuppressive medications within 14 days prior to administration of study drugs. Inhaled or topical steroids and adrenal replacement doses >10 mg daily prednisone equivalent are permitted in the absence of active autoimmune disease.
- 8) Female subject who is pregnant, breastfeeding, or is considering becoming pregnant during the study or for approximately 31 weeks after the last dose of study drugs.
- 9) Male subject who is considering fathering a child or donating sperm during the study for approximately 31 weeks after the last dose of study drugs.
- 10) Prior participation in a rovalpituzumab tesirine clinical trial, or known hypersensitivity to rovalpituzumab tesirine or excipient contained in the drug formulation, unless undergoing retreatment with rovalpituzumab tesirine in the context of this protocol.
- 11) Known hypersensitivity to any corticosteroid or excipients contained in the drug formulations.

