5.6 Required Premedication and Post-medication

All subjects enrolled will receive premedication consisting of dexamethasone orally (PO) at 8 mg BID given on Day -1, Day 1 (the day of dosing), and Day 2 of each rovalpituzumab tesirine cycle. Dexamethasone will be provided through a subject's local prescription by investigator or other provider (i.e., dexamethasone will not be provided by the sponsor). When dexamethasone is not available, the glucocorticoid-equivalent dose of an alternate corticosteroid may be administered. Parenteral (e.g., intravenous, IV) administration may be substituted for per os (by mouth/orally, PO) at the discretion of the investigator.

On Day 1 of each rovalpituzumab tesirine cycle, the first dose of dexamethasone of the day must be taken at least 30 minutes, but no more than 4 hours, prior to the rovalpituzumab tesirine infusion. In the event that a subject arrives for administration of study drugs on Day 1, but has not taken any or all required dexamethasone doses on Day -1 and/or Day 1, study drug administration may proceed, at the investigator's discretion, after administration of a parenteral corticosteroid dose equivalent to the total missed dexamethasone dose prior to administration of study drugs. For instance, subjects who missed 1, 2, or 3 dexamethasone doses could receive 43 mg, 85 mg, or 128 mg methylprednisolone IV, respectively, prior to proceeding with administration of study drugs. If a subject misses any dose(s) of dexamethasone prior to these visits, the medical monitor may be consulted if additional guidance is needed.

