6.4.2 Day 1 Visit (±2 days) of Each Cycle

If Screening activities occur within 1 calendar day prior to Cycle 1 Day 1, the following pre-dose assessments do not need to be repeated at the Cycle 1 Day 1 Visit: physical examination, ECOG performance status, local safety labs (CBC with differential, chemistries, coagulation tests, urinalysis, and pregnancy test), and disease assessment with tumor response on cycles where imaging is required.

Day 1 procedures may be performed up to 2 calendar days prior to dosing of study drugs. Results from local clinical laboratory tests (at least CBC with differential and serum chemistry panel)

and disease assessment with tumor response on cycles where imaging is required must be available prior to dose administration. All assessments must occur prior to dosing (Appendix 13.1). Imaging report confirming measurable or evaluable disease from the central reader will be provided to determine eligibility prior to enrollment.

The following will be performed on the Day 1 Visit of each cycle:

- Physical examination (Section 7.7.1)
- Vital signs – within 30 minutes prior to the infusion, and then post-infusion at 30 minutes (± 10 minutes), 2 hour (± 15 minutes), and 4 hour (± 30 minutes) for Cycles 1 and 3 only. For all other cycles, vital signs should be collected at least 30 minutes (± 10 minutes), but no longer than 4 hours prior to infusion (Section 7.7.2). Post-infusion vitals do not need to include weight. Weight needs to be collected only once prior to infusion and does not need to be collected within 30 minutes prior to infusion.
- Urinalysis (Section 7.7.3)
- Pregnancy test (urine) (Section 7.7.3) for women of child-bearing potential
- Triplicate ECG prior to infusion of rovalpituzumab tesirine and then post-infusion at 30 minutes ± 10 minutes (only done on Cycles 1 and 3) (Section 7.7.4). Triplicate ECG should be performed prior to PK draw.
- Echocardiogram (only performed at Cycles 1 and 3 (cycles where rovalpituzumab tesirine is administered) (Section 7.7.5)
- ECOG performance status (Appendix 13.3)
- Fluid Retention Questionnaire with daily weight diary accountability (Cycles 1, 2, 3, and 4) (Section 7.7.7)
- Record all AEs and SAEs (Section 7.6)
- Record concomitant medications
- Blood sample collection for:
 - CBC with differential (Section 7.7.3)
 - Serum chemistries (Section 7.7.3)
 - Coagulation tests (Section 7.7.3)
 - Rovalpituzumab tesirine PK (Section 7.3)

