10.3.5 Safety Analyses

Safety endpoints will be summarized using data from the Safety Set. Safety analyses will involve examination of the incidence, severity, and type of TEAEs reported, changes in vital signs and laboratory test results from baseline (the assessment prior to first dose) to specified time points throughout the study, and concomitant medications use.

At least 1 laboratory or other safety-related assessment subsequent to at least 1 dose of study drug is required for inclusion in the analysis of a specific safety parameter. To assess change from baseline, a baseline measurement is also required.

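### Does a baseline sample taken after dexamethasone premedication has begun spoil the change-from-baseline summaries?

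*Combined protocol and SAP*

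**What the plan says.** Section 10.3.5 sets the safety analysis as an examination of "changes in vital signs and laboratory test results from baseline (the assessment prior to first dose) to specified time points throughout the study". Section 10.3.5.2 applies this to laboratory data: values and change from baseline at each visit, with shift tables for chemistry and hematology. Section 10.3.6 plans absolute and percent change from baseline for blood soluble markers and circulating tumour cells, and gives no baseline definition of its own. Sections 10 and 10.3.6 leave further detail to the SAP, and the supplied document contains no SAP text that narrows the definition.

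On premedication, Section 5.6 gives every subject "premedication consisting of dexamethasone orally (PO) at 8 mg BID given on Day -1, Day 1 (the day of dosing), and Day 2". This holds for the cycles with rovalpituzumab tesirine, which in the planned schedule are Cycles 1 and 3. The first Day 1 dose comes between 30 minutes and 4 hours before the infusion. Two provisions add variation. One is substitution: "When dexamethasone is not available, the glucocorticoid-equivalent dose of an alternate corticosteroid may be administered". The other covers a subject who "has not taken any or all required dexamethasone doses on Day -1 and/or Day 1, study drug administration may proceed"; here the investigator decides, and a parenteral replacement is given first.

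On sampling, Section 6.4.2 states "Day 1 procedures may be performed up to 2 calendar days prior to dosing of study drugs". It also says "If Screening activities occur within 1 calendar day prior to Cycle 1 Day 1, the following pre-dose assessments do not need to be repeated", and the list that follows includes the local safety laboratory tests.

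**The concern.** Two scheduled samples precede the first dose of study drug: the Screening sample and the Cycle 1 Day 1 pre-dose sample. Section 10.3.5 does not say which one counts. If the usual choice is made (the last value before study drug), the baseline sample often follows the start of dexamethasone, by an amount that varies between subjects. Most later visits are in cycles, or parts of cycles, without it. With no control arm, a shift caused by the end of premedication could not be told apart from a shift caused by the regimen.

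The documents lend this some weight. Exclusion criterion 7 in Section 4.2 rules out conditions requiring "systemic treatment with corticosteroids (>10 mg daily prednisone equivalent) or other immunosuppressive medications within 14 days prior to administration of study drugs", so the protocol itself counts systemic steroids among immunosuppressive drugs, and Section 2.3 has an exploratory objective on immune biomarkers. What would be at stake is the reading of change and shift tables for steroid-sensitive parameters. That differential counts and glucose are steroid-sensitive is an assumption; the documents do not say so.

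**Working it through.** **Inputs.** Dexamethasone 8 mg per dose, twice daily from Day -1, with one Day 1 dose before the infusion (Section 5.6). Day 1 procedures allowed from Day -2 (Section 6.4.2). Screening from Day -14 (Section 6.3). Premedication in Cycles 1 and 3 only (Section 6.4.1 and Appendix 13.1).

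**Step 1: planned doses before the first infusion.** Two on Day -1 plus one on Day 1: 3 × 8 mg = 24 mg. The protocol's own example confirms the count: "subjects who missed 1, 2, or 3 dexamethasone doses could receive 43 mg, 85 mg, or 128 mg methylprednisolone IV, respectively". The implied ratio is 128 / 24 = 5.33 mg methylprednisolone per mg dexamethasone. Applied to 8, 16 and 24 mg it gives 42.7, 85.3 and 128.0 mg, which round to the stated 43, 85 and 128.

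**Step 2: doses taken before a baseline laboratory sample.**

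| Day of sample | Doses before it | Dexamethasone |
|---|---|---|
| Day -2 or earlier | 0 | 0 mg |
| Day -1 | 0 to 2 | 0 to 16 mg |
| Day 1, all doses taken | 2 to 3 | 16 to 24 mg |
| Day 1, doses missed | 0 to 3, or a replacement steroid | 0 to 24 mg, or the equivalent |

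The range of 0 to 3 doses is therefore correct for laboratory samples. Vital signs vary less. Section 6.4.2 times the Cycle 1 reading within 30 minutes before the infusion, after all three planned doses. The Appendix 13.1 notes give 30 minutes to 4 hours before it, which allows two or three.

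**Step 3: later visits.** CBC and chemistry visits after baseline through Cycle 5 Day 1 are C1D8, C1D15, C2D1, C3D1, C3D8, C3D15, C4D1 and C5D1, so 8. All but C3D1 lie outside scheduled premedication: 8 - 1 = 7.

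**Step 4: what 7 of 8 does and does not show.** It counts visits outside the premedication schedule. It does not count mismatched comparisons, for three reasons.

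- The 2-day allowance in Section 6.4.2 covers the Day 1 visit of every cycle. A Cycle 3 Day 1 sample may itself follow 0 to 3 doses, so its difference from baseline can be anything from 0 - 3 = -3 to 3 - 0 = +3 doses. It is not a reliable like-for-like visit.
- If the baseline sample was drawn on Day -2, the seven other visits are the matched ones as far as premedication goes (0 doses at baseline, none scheduled near the visit).
- Being outside premedication is not the same as being free of steroids. Section 5.7.2 permits up to 20 mg prednisone equivalent a day and intermittent high-dose courses. Section 8.3.1 and Appendix 13.7 add treatment courses for effusions and immune-mediated events.

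**Step 5: size of the effect.** The documents give no steroid effect, in size or direction, for any laboratory value or marker. None can be computed from them.

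**Step 6: results that use this baseline.** Response rate, adverse event incidence, values by visit, out-of-range listings and the sample size do not. Premedication is the same in all cohorts, so it introduces no planned difference between them. One DLT criterion in Section 3.1.1 refers to recovery to baseline, but as an alternative to recovery to Grade 1 or below. It can matter only for a subject whose baseline is worse than Grade 1, and nothing ties it to the analysis baseline of Section 10.3.5.

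**The case for a change.** The strongest case for a change is that the wording is open, the usual reading is the one that produces variable steroid exposure, and the remedy is cheap. Screening samples for blood counts, chemistry, soluble markers, flow cytometry and RNA are already scheduled. A few sentences and one more set of tables would give a baseline taken before any premedication.

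Part of this stands. The text does not name the sample, and dexamethasone appears in the list of treatments administered (Section 5.1), so even the reference to a first dose could be worded more tightly.

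The remedy, however, does not clearly give a better baseline. A Screening sample may be up to 14 days older. It lies nearer to previous anticancer therapy, which need have ended only two weeks before (Sections 4.1 and 5.7.3). It may also come from a subject on a permitted steroid dose, since the exclusion applies only above 10 mg prednisone equivalent. With steroids also permitted on study, such a baseline would not isolate the regimen's effect. Nor can it serve every parameter: circulating tumour cells and tumour DNA have no Screening blood sample. In the other direction, the substitution of Screening results for Cycle 1 Day 1 covers only the local safety tests, so the soluble-marker, flow cytometry and RNA samples at Cycle 1 Day 1 are still due.

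**Conclusion.** No change to the plan is needed. The wording leaves a small gap that analysts fill by convention: baseline is the last value before the first dose of study drug. For local safety tests that is the Cycle 1 Day 1 pre-dose sample, or the Screening sample that replaces it when drawn no more than one calendar day earlier.

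The demonstrated extent is an exposure range at baseline of 0 to 3 doses (0 to 24 mg dexamethasone, or a substitute). No distorted result has been shown, because no effect size is available and the tables affected are descriptive. The choice between a recent baseline partly under premedication and an older one nearer to previous treatment is a fair trade-off. Where Screening samples exist, the second summary can be derived later without new data collection.

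This rests on two assumptions: that a first dose in Section 10.3.5 means study drug, and that change-from-baseline tables are read alongside the raw values by visit. If a decision were ever to rest on change from baseline in an immune marker, the steroid timing would deserve a supportive summary at that point. Nothing in the documents ties a decision to such a change.

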10.3.5.1 Treatment-Emergent Adverse Events

TEAEs reported during the study will be coded using a MedDRA dictionary. Incidence of TEAEs will be summarized by cohort.

10.3.5.2 Clinical Laboratory Evaluation

Laboratory parameters will be summarized by cohort at each visit. Each summary will include the values of the laboratory parameters and their change from baseline. Shift tables from baseline will be presented for laboratory values in the chemistry and hematology panels. A listing will be provided for out of normal range as well as clinically significant abnormal lab values.

10.3.5.3 Vital Signs

Vital signs, including pulse, blood pressure, temperature, height, and body weight will be summarized by cohort and time point. For each assessment of vital signs, change and percent change in vital signs from baseline will be summarized by cohort.

10.3.5.4 ECOG Performance Status

ECOG performance status will be summarized for each visit by cohort. Shifts from baseline to the best and worst post-baseline score may be tabulated.

10.3.5.5 Electrocardiogram

ECG status will be summarized for each scheduled visit by cohort. Shifts from baseline may be tabulated. Additionally, ECG parameters will be described using the five-number summary (mean, standard deviation, median, minimum, and maximum).

10.3.5.6 Echocardiogram

Change from baseline of echocardiogram parameters will be described using the five-number summary (mean, standard deviation, median, minimum, and maximum).

10.3.5.7 Concomitant Medications

Concomitant medications will be classified according to the anatomical therapeutic chemical (ATC) codes in the World Health Organization Drug (WHODRUG) dictionary. The incidence rate of each coded concomitant medication will be tabulated by cohort. The table will be sorted by the incidence use of the entire sample.

10.3.6 Pharmacokinetic and Pharmacodynamics Analyses

Concentrations of rovalpituzumab tesirine, nivolumab, and ipilimumab will be summarized using descriptive statistics.

Data from the PK-Evaluable set may also be used in the analysis of PK and exposure-PD analyses. In addition, the PK of rovalpituzumab tesirine, may also be characterized using population methods.

The incidence and timing of ATAs to study drugs will be summarized by descriptive statistics. The possible effects of ATA on PK, efficacy and safety may be explored.

The five-number summary will be used to describe absolute and percent change from baseline in IHC, blood soluble markers (such as soluble DLL3 or █████ and CTCs. Regressions may be performed as appropriate. Exploratory analyses may be performed to evaluate a possible correlation between each of these endpoints and disease response and/or toxicities. Additional analyses may also be performed. Details will be provided in the Statistical Analysis Plan.

11. Ethical and Regulatory Considerations

GCP requires that the clinical protocol, any protocol amendments, the IB, the ICF and all other forms of subject information related to the study (e.g., advertisements used to recruit subjects) and any other necessary documents be reviewed by an IEC/IRB. The IEC/IRB will review the ethical, scientific and medical appropriateness of the study before it is conducted. IEC/IRB approval of the protocol, ICF, and subject information and/or advertising, as relevant, will be obtained prior to the authorization of drug shipment to a study site.

Any amendments to the protocol will require IEC/IRB approval prior to implementation of any changes made to the study design. The investigator will be required to submit, maintain and archive study essential documents according to ICH GCP.

Any SAEs that meet the reporting criteria, as dictated by local regulations, will be reported to both responsible Ethics Committees and Regulatory Agencies, as required by local regulations. During the conduct of the study, the investigator should promptly provide written reports (e.g. ICH Expedited Reports, and any additional reports required by local regulations) to the IEC/IRB of any changes that affect the conduct of the study and/or increase the risk to subjects. Written documentation of the submission to the IEC/IRB should also be provided to the sponsor.

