2.3 Exploratory Objectives

- To explore the expression of DLL3 and PD-L1 in SCLC and their relationship to clinical outcome during treatment
- To explore the pharmacokinetics (PK) of and incidence of anti-therapeutic antibodies (ATA) against rovalpituzumab tesirine, nivolumab, and ipilimumab
- To explore the effect of study drug regimen on disease and immune biomarkers

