4.1 Inclusion Criteria

- 1) Written informed consent.
 - a) Must have signed and dated an IRB/IEC approved written informed consent form (ICF) in accordance with regulatory and institutional guidelines. This must be obtained before the performance of any protocol-related procedures that are not part of normal patient care.
 - b) Must be willing and able to comply with scheduled visits, treatment schedule, laboratory testing, and other requirements of the study.
- 2) Target population
 - a) Histologically or cytologically confirmed extensive-stage SCLC with PD after at least one platinum-based chemotherapeutic regimen.
 - b) Measurable disease, defined as at least 1 tumor lesion ≥ 10 mm in the longest diameter or a lymph node ≥ 15 mm in short-axis measurement assessed by computerized tomography (CT) scan (RECIST v1.1) or evaluable disease.
 - c) Availability of representative baseline tumor tissue (archived or on-study biopsy) suitable for immunohistochemistry testing. Up to the first 12 subjects of each study cohort must be DLL3 positive per IHC (Immunohistochemistry) assay criteria, based on central assessment prior to enrollment.
 - d) ECOG performance status of 0 or 1. See Appendix 13.3 for conversion of performance status using Karnofsky scales, if applicable.
 - e) Minimum life expectancy of at least 12 weeks.

- f) Asymptomatic central nervous system (CNS) metastases, if present, must be stable, with or without previous treatment, in the absence of corticosteroids for at least 2 weeks prior to initiation of study drugs.
 - g) Recovery to Grade 1 of any clinically significant toxicity (excluding alopecia) prior to initiation of administration of study drugs.
 - h) Satisfactory laboratory parameters:
 - i. Absolute neutrophil count (ANC) $\geq 1,000/\mu\text{L}$.
 - ii. White blood cell count (WBC) $\geq 2,500/\mu\text{L}$.
 - iii. Platelet count $\geq 100,000/\mu\text{L}$.
 - iv. Hemoglobin ≥ 9.0 g/dL.
 - v. Total bilirubin ≤ 1.5 x upper limit of normal (ULN) or ≤ 3 x ULN for subjects with Gilbert's disease.
 - vi. Alanine aminotransferase (ALT) and aspartate aminotransferase (AST) ≤ 3.0 x ULN (≤ 5 x ULN if evidence of hepatic involvement by malignant disease).
 - vii. Creatinine ≤ 1.5 x ULN or estimated glomerular filtration rate (eGFR) ≥ 40 mL/min/1.73m².
 - viii. Albumin ≥ 3 g/dL.
 - iv. Lipase ≤ 1.5 x ULN. Subjects with Lipase > 1.5 x ULN may enroll if there are neither clinical nor radiographic signs of a pancreatitis.

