10.3 Planned Analyses

As a general strategy, continuous efficacy and safety endpoints will be summarized using the five-number summary (mean, standard deviation, median, minimum, and maximum). Frequency distributions (counts and percentages) will be used to summarize categorical endpoints.

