- 38) Tumor Tissue consists of procurement of archived, representative tumor tissue, or an optional fresh tumor biopsy, if accessible for DLL3 and PD-L1 testing. Any remaining tissue may be utilized for additional biomarker research and exploratory studies including, but not necessarily limited to, assessment of tissue for nucleic acid or protein based biomarkers to understand drug sensitivity and resistance, biology of SCLC, and to develop new diagnostic tests. With consent from the subject, tumor tissue may be obtained prior to the screening period (during the prescreening portion of the study) and tested for DLL3 and PD-L1 expression. Up to the first 12 subjects enrolled into each cohort must be DLL3 positive. For any subjects who did not complete a prescreening visit, this will be done at screening.
- 39) Optional collection of tumor tissue at progression.
- 40) [REDACTED]
- 41) Blood soluble markers sample will be tested for various soluble markers that may include but are not limited to chemokines or cytokines, soluble DLL3, and soluble tumor-specific biomarkers such as [REDACTED]. Samples will be collected pre-dose at designated visits, and again during retreatment cycles at predose of C1D1, C2D1, C3D1.
- 42) Flow cytometry consists of the collection of blood for characterization of immune cell subsets. Samples will be collected pre-dose at designated visits.
- 43) Peripheral blood RNA consists of whole blood RNA for assessment of analytes that may reflect the PD effects of rovalpituzumab tesirine and/or nivolumab, including [REDACTED]. Samples will be collected pre-dose at designated visits.
- 44) CTC collection includes a sample for exploratory analyses of CTC-associated biomarkers such as DLL3, implemented only at specific sites based on feasibility.
- 45) CTC collection to occur pre-dose on Day 1 of Cycles 1 and 5.
- 46) Genotyping includes blood and/or tumor sample for possible assessment of genes for genetic lesions and/or polymorphisms which may influence the safety or efficacy response to the study drugs. Such genes may include but are not necessarily limited to [REDACTED].
- 47) Serosal Fluid entails procurement, where feasible, of any pericardial, pleural and/or ascitic fluid collected as part of routine care (e.g. as part of a therapeutic thoracentesis, pericardiocentesis, or paracentesis), for possible PK, PD, and/or biomarker testing.
- 48) ctDNA collection to occur pre-dose on Day 1 of Cycle 1 and EOT.

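### Mean percent change from baseline, one of the exploratory biomarker statistics in Section 10.3.6, has no value at a zero baseline and is biased upward when nothing has changed

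*Combined protocol and SAP*

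**What the plan says.** Section 2.3 gives the third exploratory objective as "To explore the effect of study drug regimen on disease and immune biomarkers". The analysis is in Section 10.3.6: "The five-number summary will be used to describe absolute and percent change from baseline in IHC, blood soluble markers", and the sentence goes on to name CTCs. Section 10.3 defines the "five-number summary (mean, standard deviation, median, minimum, and maximum". Each marker therefore gets five statistics for absolute change and the same five for percent change. The plan does not say which of them leads.

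Section 10.3.6 has no rule for a zero or below-quantification baseline and no log or ratio scale. It allows regressions and exploratory correlations of these endpoints with response or toxicity, and it closes: "Details will be provided in the Statistical Analysis Plan". The document as supplied contains no separate SAP text with those details.

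A zero baseline is possible for two of the three marker groups:

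- **CTCs** are counts. The notes to the Cohort 1 schedule in Appendix 13.1 say "CTC collection to occur pre-dose on Day 1 of Cycles 1 and 5", and the schedule also marks the end-of-treatment visit.
- **IHC** covers DLL3 and PD-L1. Section 4.1, criterion 2c, says "Up to the first 12 subjects of each study cohort must be DLL3 positive per IHC"; subjects enrolled after that may score low or zero on DLL3. PD-L1 expression is not an eligibility criterion.

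**The concern.** Percent change divides by a noisy baseline, and this causes two separate problems.

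First, at a baseline of zero the quantity does not exist. Those subjects leave the percent-change summary, and they are not a random subset. Having started at the floor, they can only stay or rise.

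Second, an arithmetic mean treats a doubling (+100%) and a halving (−50%) as unequal, although on a ratio scale they cancel. A few subjects with a small baseline by chance then dominate both the mean and the SD. In cohorts of 6 to 30 without a control arm, no concurrent group would show that a mean rise is an artefact. The same values could carry into the correlations with response and toxicity that Section 10.3.6 allows.

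**Working it through.** The plan states no biomarker effect size, variance or power, so there is no figure of its own to reproduce. The check asks what each planned statistic shows when the true change is nil.

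**Inputs.** From the document: the five-number summary of absolute and percent change (Sections 10.3 and 10.3.6) and up to about 30 subjects per cohort (Section 10.1). Assumed, because the document gives no values: within-subject log-SD s of 0.2 to 1.0, and the CTC distributions below.

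**Two-subject example.** One subject doubles and one halves. Mean percent change = (100 − 50)/2 = +25%. Geometric mean change = √(2 × 0.5) − 1 = 0%.

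**Soluble markers, lognormal, no change.** Let log Y₀ and log Y₁ share a subject mean and have independent errors of SD s. Then log(Y₁/Y₀) is normal with mean 0 and variance 2s². So E[Y₁/Y₀] − 1 = exp(2s²/2) − 1 = exp(s²) − 1, while the median ratio and the geometric mean ratio are both 1. The last three columns are simulated (20,000 cohorts of 30):

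| s | exp(s²) − 1 | Cohorts with mean percent change above 0 | Average of cohort median percent changes | Mean absolute change* |
|---|---|---|---|---|
| 0.2 | +4.1% | 77% | +0.2% | 0.001 |
| 0.3 | +9.4% | 86% | +0.5% | 0.000 |
| 0.5 | +28.4% | 95% | +1.3% | −0.003 |
| 0.7 | +63.2% | 98.5% | +2.5% | 0.005 |
| 1.0 | +171.8% | 99.6% | +5.6% | 0.011 |

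*In marker units, with the population median set to 1.

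The geometric mean change stayed between −0.1% and +0.2% throughout.

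**CTCs, gamma-Poisson counts, no change.**

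- *Poisson noise only* (mean 5 to 50, gamma shape 0.5 to 1.0): 2% to 30% of subjects have a zero baseline. Among the rest, mean percent change is +5.5% to +13.3% and the median is 0%.
- *With added within-subject log-SD 0.5* (mean 5 to 30, shape 0.3 to 1.0): 4% to 44% have a zero baseline. Among the rest, mean percent change is +25% to +39% and the median runs from about −13% to 0%. In all subjects, mean absolute change is −0.05 to +0.10 cells and median absolute change is 0.

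**Who drops out.** In the Poisson-only setting with mean 5 and shape 0.5, the 30.1% with a zero baseline rise by 0.46 cells on average and the other 69.9% fall by 0.20. Over everyone, 0.301 × 0.46 − 0.699 × 0.20 = 0.138 − 0.140, which is about 0. Absolute change in all subjects balances; percent change sees only the second group.

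**A log(x+1) ratio for CTCs.** With no change its geometric mean is 1.00. With a true halving imposed in the six settings with added noise, it gives 0.54 to 0.74 in place of 0.50, so it understates the fall when counts are low.

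**The case against.** The strongest objection is that the plan does not rely on mean percent change. The same sentence plans absolute change, which is defined at zero and averages about zero under no effect, and the five-number summary includes the median. Printing mean, median, minimum and maximum together also lets a reader see skew. The objective is exploratory, no test or decision rule uses these summaries, and the one numerical go-forward criterion in the protocol is the lower confidence bound for response rate against 23% (Section 1.4). Details are deferred to the SAP, and the sizes above rest on assumed variability.

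All of that stands, and it limits the point. A reader might infer that Section 10.3.6 misstates the regimen's effect on biomarkers, or that a rise from zero is never counted. The document supports neither: the absolute-change summary counts such rises, and most of the planned statistics are free of the upward bias.

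The objection does not rescue the mean of percent change itself. Section 10.3.6 commits to that statistic, so this is more than a missing detail.

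A reader might also attach the age of the baseline tissue to this point, since the schedule notes say "Tumor Tissue consists of procurement of archived, representative tumor tissue, or an optional fresh tumor biopsy" and later tissue is optional at progression. That is a separate question. It affects any change statistic, including absolute change.

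**Conclusion.** The point holds as a modest one about a single exploratory statistic. That mean percent change is undefined at zero and biased upward under no change is a matter of arithmetic and does not depend on this trial's data. Its size here cannot be fixed from the document. For soluble markers it is about +9% to +63% if s lies between 0.3 and 0.7 with independent lognormal errors. For CTCs it was positive in every setting tried, from +5.5% to +39%, depending on the noise model.

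Median percent change is a sound companion for lognormal markers. It is less dependable for CTCs, where leaving out zero baselines can pull it below zero at low counts. Absolute change in all paired subjects is unaffected in either case.

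**What to change.** In the SAP, or in Section 10.3.6 if it is amended:

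- **Soluble markers:** replace the mean and SD of percent change with the geometric mean fold change from baseline (the back-transformed mean log ratio) and its 95% CI. Fix in advance how values below the assay's quantification limit enter the ratio.
- **CTCs and IHC:** drop mean percent change. Keep absolute change, shown as median and range, in all subjects with paired samples. Report the number with a zero baseline and the shifts from 0 to above 0 and from above 0 to 0.
- **Optional for CTCs:** a log(x+1) ratio as a supplement only, with the constant fixed in advance and a note that it attenuates true changes at low counts.

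The cost is SAP wording and minor extra programming. No data collection changes. The one downside is that fold change is slightly less familiar to readers than percent change.
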